### **Report type**

Recruitment;

Baseline characteristics of the participants;

Completeness of data (visits completed, % of expected forms submitted, % of submitted forms passing edit);

Missing data;

Summary of adverse events (including duration, severity, seriousness, relatedness, action taken, resolution);

Descriptive information for each endpoint without statistical testing;

Participant retention; and

Quality control analyses for primary outcome.

### **Recruitment rates and adherence inclusion/exclusion criteria, and ethnic diversity goals:**

Recruitment progress, inclusion/exclusion criteria, and diversity goals will be reviewed at each meeting. This review will ensure that project deadlines are being met, that participants meet eligibility criteria, and that the ethnic diversity goals outlined in the grant proposal are being met.

### **Adherence to study protocols:**

The principal investigator will: direct creation of all study protocols and will be involved in trainings and supervision of all study staff. Quality control will be conducted in all phases of the project.

### **Adverse events:**

Participants who report conditions during the screening phase that could create a safety concern while receiving the intervention will be excluded. Adverse events that occur during the intervention will be assessed, recorded, and followed up until resolved. Safety monitoring procedures will be documented in a standard protocol and overseen by the PI and program director. Any adverse events will be immediately reviewed by the program director. The safety officers will be informed during monthly reports for all adverse events. Serious adverse events will be communicated immediately to the safety officers. The NIH and UConn IRB be notified immediately in the event of serious adverse event. Any death of a study participant will be reported to the NIH and UConn IRB whether or not it appears to be related to the study.

The adverse event report will include a listing of adverse events including duration, severity, seriousness, relatedness, action taken, and resolution. This information will be presented unblinded. A significant increase in the rate of adverse events in one treatment group would be cause for concern for the safety of participants in the study.

### **Participant retention**

Engagement will be recorded throughout the study. Engagement data will be provided in a report to the safety officers.

### **Data Security:**

The databases will be maintained on UConn servers where security will be maintained through access controls. The program director will control the database and surveys and will allow access to necessary staff. Staff wanting access to identifiable data will need to: have prior IRB approval to be on the project, apply for a REDCap account, be approved by the program director, and utilize a password for login.

**Data review (completeness/outliers):**

Data reports will be reviewed by the data manager, project director, statistician, and PI. Reports will include completeness of data (visits completed, online engagement, % of expected forms submitted, % of submitted forms passing edit); missed visits and missing information within visits; descriptive information for each endpoint (change in weight and physical activity) without statistical testing; and quality control analyses for primary outcome (change in weight).

**Privacy/Confidentiality Part 1:** *[Explain how the privacy interests of participants will be maintained during the study (note that **privacy pertains to the individual not to the data**). Describe how data will be coded. Do not use the any potentially identifiable information such as initials of participants as part of the code. Explain how long data will be kept in an identifiable format and how long de-identified data will be retained. Explain how long the master key or audio or video recordings obtained, will be kept. Consider whether keeping de-identified data will be retained indefinitely and whether participants may be contacted for a follow-up study (explain procedures to retain identifiable contact data is kept.)]*

REDCap will be used for data entry and NVivo, SPSS, and SAS will be used for the data extraction. The database will be maintained on UConn servers where security will be maintained through access controls. Files will be managed by the data manager and project director, who will control user access and rights. For each user, REDCap will require a REDCap profile, username and password to enter the program. Staff will only have access to the database if the data manager has given them access. To protect research staff privacy, they will each use Google Voice to send the reminder text messages to participants. Google Voice is a free app that provides you with a phone number that is not the same as your personal number. The research assistants that have Google Voice on their phone will ensure that their phone is password protected. Also, they will not save any contact information into the Google Voice app. UConn IRB and their representatives, and study personnel will have access to the research data, as will the study sponsor if requested. When discussing the referral process to participants, we will not disclose names to either the referred person or to the person who referred others to the study. If someone is compensated for their referral, we will not tell them who it was that referred them. Participants will be assigned an ID number, which will link them to their study data. The ID number will be 3-4 numerical characters representing the number of participants in the study. PHI fields will be stored in a separate form from other data collection forms. Data will be completely de-identified once the study is complete and extraction data has been analyzed. At this time the link between participant identity and study data will be destroyed. Study data in the form of hard copies will be stored in a locked file cabinet managed by the program director and will be destroyed 3 years after completion of the study.

Data from ineligible participants:

Contact information will be stored in a file with an indication that they are not eligible. However the data collected from the screening, including reason ineligible, will be stored in a separate de-identified file.

*If identifiable, sensitive information (illegal drug use, criminal activity, etc.) will be collected, state whether a Certificate of Confidentiality will be obtained.*

*Be sure to state whether any limits to confidentiality exist (e.g. mandated reporting) and identify any external agencies (study sponsor, FDA, etc.) that will have access to the data.*

*If participants will be screened, describe the plans for storage or destruction of identifiable data for those that failed the screening.]*

**Privacy/Confidentiality Part 2: Complete the Data Security Assessment Form:** *[This form IS REQUIRED for ALL studies. The form is available here - <http://research.uconn.edu/irb/irb-forms-infoed/>. This form will be used to assess procedures for protecting confidentiality of data collected during the study and stored after closure. It will also be used to assess plans for storage and security of electronic data in accordance with University Best Practices. Review the document proving tips to complete the form located at <http://content.research.uconn.edu/pdf/storrs/rcs/irb/TipsDataSecurityAssessmentForm.docx>.*

## **Informed Consent**

**As PI, you are responsible for taking reasonable steps to assure that the participants in this study are fully informed about and understand the study. Even if you are not targeting participants from “Special Populations” as listed on page 4, such populations may be included in recruitment efforts. Please keep this in mind as you design the Consent Process and provide the information requested in this section.**

**Consent/permission Setting:** *[Describe the consent/permission process including who will obtain it, where and when will it be obtained, and how much time participants will have to make a decision. Describe how the privacy of the participants will be maintained throughout the consent process.]*

A signed consent waiver is being requested for this study. Participants will review an informational page before completing the initial survey screener. They will have as much time as needed to review the information sheet and email/call staff with questions. They may also decide not to proceed with the survey. Consent will be reviewed during the telephone screening by research assistants/coordinators trained in the consent process.

*State whether an assessment of consent/permission materials will be conducted to assure that participants understand the information (may be warranted in studies with complicated study procedures, those that require extensive time commitments or those that expose participants to greater than minimal risk).]*

**Capacity to Consent:** *[Describe how the capacity to consent will be assessed for participants with limited decision-making capacity, language barriers or hearing difficulty. If a participant is incapable of providing consent, you will need to obtain consent from the participant’s legal guardian (please see the IRB website for additional information).]*

To be able to actively participate in the study, participants must be adults without impaired decision making ability that are able to speak and read English. The consent process will include a discussion of the participants understanding of what participating in research means including their rights as a research participant, the protocol, as well as risks and potential benefits to participating in the study. If research personnel obtaining consent believes there is a concern regarding a participant understanding participation will be discussed with the program director who will determine whether to exclude the participants on this basis.

**Parent/Guardian Permission and Assent:** *[If enrolling children, state how many parents/guardians will provide permission, when the child’s assent will be obtained and if assent will be written or oral. Provide a copy of the script to be used if oral assent will be obtained. For longitudinal studies, assent may happen at several points during the study. ]*

N/A

**Documentation of Consent:** *[Specify the forms that will be used for each participant population, i.e., adult consent form, surrogate consent form, parental permission sheet, child assent form (written form or oral script) or an information sheet. Copies of all forms should be attached to this application in the same format that they will be given to participants (templates and instructions are available on the IRB website).]*

An online information sheet will be used for the study participants. Participants will select an item on the survey after reviewing the online consent if they choose to participant or not.

**Waiver or Alteration of Consent:** *[The IRB may waive or alter the elements of consent in some minimal risks studies. If you plan to request either a **waiver of consent** (i.e., participants will not be asked to give consent), an **alteration of consent** (e.g., deception) or a **waiver of signed consent** (i.e., participants will give consent after reading an information sheet), please answer the following questions using specific information from the study:]*

*Waiver (i.e. participants will not be asked to give consent) or alteration of consent (e.g. use of deception/incomplete disclosure in research):*

- *Why is the study considered to be minimal risk?*
- *How will the waiver affect the participants' rights and welfare? The IRB must find that participants' rights are not adversely affected. For example, participants may choose not to answer any questions they do not want to answer and they may stop their participation in the research at any time.*
- *Explain why the research could not be practicably carried out without the waiver. For studies that involve deception, explain how the research could not be done if participants know the full purpose of the study.*
- *Since we are recruiting nationally, an electronic consent process is most efficient for participants and study staff. Explain why the research could not be practicably carried out without using identifiable private information and/or identifiable biospecimens.*
- *How will important information be returned to the participants, if appropriate? For studies that involve deception, indicate that participants will be debriefed and that the researchers will be available in case participants have questions.*
- *Indicate if the waiver/alteration as noted above is applicable to the entire study or to a portion of the study.*

*Waiver of **signed** consent (i.e. , no signature, participants give consent only after reading an information sheet). Tip: if the investigator will obtain information through oral or written communication with the prospective participant or if the investigator will obtain private identifiable information or identifiable biospecimens by accessing records, then a waiver of signed consent is NOT required.,:*

We are requesting a waiver of signed consent to recruit participants across the US for an online study.

- Why is the study considered to be minimal risk?  
  
The study is minimal risk because it includes three brief surveys and following a social media feed. The probability of harm or discomfort from three surveys and following a social media feed is no greater than ordinarily encountered in daily life.
- Does a breach of confidentiality constitute the principal risk to participants? Relate this to the risks associated with a breach of confidentiality and indicate how risks will be minimized because of the waiver of signed consent.

No. There would not be harm to participants if identification of participants or their responses would place them at risk of liability or be damaging to financial standing, employability, insurability, reputation, or be stigmatizing. The participants are informed that they do not have to answer any questions or interact with any portion of the Twitter or Facebook feeds if it makes them feel uncomfortable in any way is free to stop participating at any time. Participants will be invited to follow the study Twitter and Facebook feeds. They will also be asked questions in the surveys regarding demographics, tanning, impact of the messages, and their acceptability of the Twitter feed, as can be seen in the measures section. None of these measures would negatively impact their financial standing, reputation, employability, or insurability. They are also informed they do not have to respond any survey questions if they do not wish to answer. The ability to review the consent online prior to the survey limits any risks of travelling to the study site for in-person consent. During the telephone screening, we ask for permission to ask questions and indicate that they may choose not to answer.

- Would the signed consent form be the only record linking the participant to the research? Relate this to the procedures to protect privacy/confidentiality.

No. We will use approved institutional data security procedures to protect this information.

- Does the research include any activities that would require signed consent in a non-research setting? For example, in non-research settings, normally there is no requirement for written consent for completion of questionnaires.

No.

- Describe if the participants or their legally authorized representatives are members of a distinct cultural group or community in which signing forms is not the norm, the research presents no more than minimal risk of harm to subjects and there is an appropriate alternative mechanism for documenting that informed consent was obtained. Not applicable to FDA Regulated Studies.

N/A

### Statistical Analysis Plan

We summarized recruitment, retention, participation, acceptability, contamination, motivation, belief that a tan is attractive, tanning intentions, outdoor tanning, sun protection behaviors, post engagement, and persuasive impact of posts using descriptive statistics. Means and standard deviations (M[SD]) were presented for variables that were normally distributed, and medians and inter-quartile ranges (IQR) were presented for variables that were not. We compared retention, participation, and acceptability rates to our pre-determined benchmarks of >80% as a metric of feasibility. We compared perceived change in motivation for each target health behavior, intentions to outdoor tan, and number of times tanned outside by condition using Wilcoxon rank sum tests as these variables were not normally distributed. We also compared if participants outdoor tanned at follow-up using a chi-squared test. As this pilot feasibility trial was not sufficiently powered to establish efficacy on the belief that a tan is attractive or sun protection behaviors, we did not compare conditions on these variables. Data analyses were conducted using SAS 9.4 (SAS Institute, Inc, Cary, NC).

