We will post online recruitment ads which will contain a link to an online 5-minute survey containing the initial screening questions. The survey will first have a description of the study and will then have the eligibility questions. The participants recruited by Qualtrics will also complete this initial survey. If they are eligible to proceed they will be contacted by the study team to book a 10-minute telephone screening call to review the consent. Afterwards they will be emailed a 15-minute online baseline surveys including tanning behavior, sun protection behavior, and social networking use. Participants will be randomized into two conditions, one will be assigned to a sun safety challenge and the other will be assigned to a healthy lifestyle through technology challenge.

**Anticipated Study Time Frame:** *[Describe the estimated time frame of the study from anticipated start to anticipated finish. If the study will occur in more than phase include these in the time frame. Use of a table is often helpful.]*

This study will take approximately 2 hours of time for participants to complete according to the breakdown below:

Visit	Time (in minutes)
Initial Survey	5 min
Telephone Screening	10 min
Baseline survey	15 min
Webinar	30 min

Intervention Approx. 10-15 min/week for 4 weeks	60 min
Follow-up survey	30 min
Total	2.5 hours

**Design, Procedures, Materials and Methods:** *[Describe the study design, including the sequence of study procedures. Experimental procedures should be clearly described and labeled as such. If the study uses control or experimental groups, or different treatment arms, clearly describe what participation will be like for each of the groups or study arms. Tip: describe procedures in the order conducted, where they will be conducted and how long they will take to complete. The IRB strongly suggests that investigators incorporate flexibility into the study design to accommodate anticipated events (i.e. explain how missed study appointments can be made up by participants). If this study offers treatment for the participants' condition, complete the Treatment Study Supplemental Form (IRB-1C) and attach it to this application for review. Use of a table is often helpful here.*

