**Study design:**

Overview: Participation starts with an initial survey, telephone screening, and baseline survey. Eligible participants will then be randomized to one of two conditions, complete a webinar, 4-week intervention, and an end-of-study follow-up survey.

About the intervention: During the 4-week intervention, participants will be asked to create social media posts (related to the topic of the condition). These posts will be sent to the study team who will post them in our study-lead Twitter and Facebook feeds. The sun safety challenge posts will be posted in the Skin Smart Campus Initiative feed and the healthy lifestyle through technology challenge posts will be posted in the @UConnmHealth Feed.

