**Intervention:** Participants will be given the name of the feed where their posts will appear. The feeds will be public which means others may follow and content can be shared by other users not in the study. Every Monday participants will be reminded via text message to create their post for the following week and send it to the study team by Friday. They will be given access to a shared calendar to indicate their preferred day/time to for their post to appear. When a post does not meet the guidelines, we will reply to the participant with feedback and encourage them to resubmit an edited version. Participants will receive \$10 Amazon gift card per post for a maximum of 6 posts. Additionally, the participant whose post receives the most engagement, defined as likes, retweets, and replies within the first 48 hours of posting each week will receive \$50 Amazon gift card. The majority of engagement on a social media post occurs within 48 hours. The 48 hour time limit also allows all posts put up by Friday to have a 48 hour period of engagement before the week is over. Winners will be announced via email every Monday.

**Follow-Up Assessment:** Following the intervention period, participants will receive an email (in week 5) with a link to the follow-up survey which will assess indoor tanning, outdoor tanning, intention to tan indoors and outdoors, desirability of tanning and tanning alternatives, exercise and diet quality, social media use, use of health technologies, and acceptability.

*[Describe study procedures for use of interviews or focus groups if applicable. Include details such as how long each procedure will take to complete, who will be asked to participate in these procedures and where these procedures will be conducted. Provide copies of interview and focus group questions/topic areas.]*

*[If the study includes measures, survey instruments and questionnaires (including the collection of demographic data), identify each and, if available, provide references for the measures. Describe what they intend to measure (relate to purpose/hypothesis) and their psychometric properties (e.g., reliability and validity). Identify any that were specifically created for the study and attach a copy for IRB review.]*

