**Measures:**

Data collected	List of Measures	Baseline	Intervention	Follow-up	Method
Demographics	Age, gender, sexual orientation, income, employment, marital status, race/ethnicity, household composition, location	X			REDCap
Tanning behavior and sun protection	Tanning behavior and sun protection	X		X	REDCap
Intentions to Tan	Intentions to Tan	X		X	REDCap
Use of tan alternatives	Use of tan alternatives	X		X	REDCap
Exercise and dietary quality*	Block 2005 Food Frequency Questionnaire	X		X	

Social media use (by platform)	Survey questions	X		X	
Use of health technologies	Health Wearable and Health App Usage Questions	X		X	
Recruitment and Retention	Number of responses, eligible, consented participants, % participants who unfollow, % who complete follow-up	X		X	REDCap
Acceptability	Survey questions			X	REDCap
Persuasive impact for each message	Transportation Scale Short Form			X	REDCap
Engagement and dissemination of intervention messages	Engagement in feeds (likes/reactions, comments/replies)		X	X	Twitter and Facebook

*\* Will be added to the measures attachment when it is purchased.*

*[If applicable, describe the use of audiotape and/or videotape, provide justification for use and indicate if this is a requirement of participation.]*

*[If the study involves use of deception or incomplete disclosure, explain the reason why this is necessary to answer the research question(s). Complete the alteration of consent section below]*

*[Describe opportunities provided to participants to ask questions in order for them to make an informed decision regarding participation.]*

Participants will review an informational page before completing the initial survey screener. The participants have the option to end the survey at any time. At the beginning of the telephone screening, staff will review the informational page and ample time will be allowed for discussion or questions.

**Data Analysis:** *[For all studies, specify the analytic techniques the researcher will use to answer the study questions. Indicate the statistical procedures (e.g. specific descriptive or inferential tests) that will be used and why the procedures are appropriate. For qualitative data, specify the proposed analytic approaches.]*

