We will use information on recruitment yield, rates, and retention to inform the recruitment strategies and timeline for the subsequent large efficacy trial. Using t-tests, we will compare the two conditions on acceptability, persuasive impact, engagement, and content dissemination. We will also describe changes from baseline to follow-up in desirability of tanning and alternatives, outdoor tanning, intentional tanning outside, sunburns, and sun protection in the two conditions.

**Inclusion/Exclusion Criteria:** *[List ALL inclusion and exclusion criteria. Any proposed exclusion criterion based on gender (women of childbearing potential), age, or race must include justification for the exclusion.]*

Inclusion criteria: 1) Ages 18-30, 2) tanned indoors or outdoors  $\geq 1$  in the past year, 3) likelihood of indoor or outdoor tanning this summer  $> 4$  on a scale from 0-10), 4) regular user of any social media platform.

Participants will be excluded if they:

1. Do not have a smartphone;

2. Do not use a social media platform daily;
3. Did not tan indoors or outdoors at least 1 time in the past year
4. Likelihood of indoor or outdoor tanning this summer is 4 or less on the scale of 0-10
5. Older than 30
6. Younger than 18
7. Does not live in a state with an averages temperature >75 degrees in May (Must live in one of these states: California, Arizona, Oklahoma, Texas, Alabama, Arkansas, Florida, Georgia, Kentucky, Louisiana, Maryland, Mississippi, North Carolina, South Carolina, Tennessee, Virginia, West Virginia, Kansas, Missouri, Delaware, Hawaii);
8. Did not complete the screening procedures;
9. Are unable to provide consent due to mental illness or a cognitive impairment;
10. Does not speak English; or
11. Are a prisoner

*[Describe the conditions under which participants may be removed from the study, i.e., noncompliance with study rules, study termination, etc.]*

Participants will be withdrawn from the study if: they drop from participation or do not complete all screening procedures. Participants reporting that they would like to withdraw from the study will be given the option to withdraw from the study completely with no additional study contact.

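### The Wilcoxon comparisons of tanning intentions and times tanned outside leave pre-randomisation baseline values unused and come with no between-arm estimate; a supportive baseline-adjusted rank analysis would add precision at little cost (low priority)

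*SAP*

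**What the plan says.** The SAP's single analysis paragraph compares "intentions to outdoor tan, and number of times tanned outside by condition using Wilcoxon rank sum tests", giving non-normality as the reason. It names no covariate. The sentence that follows reads "We also compared if participants outdoor tanned at follow-up using a chi-squared test", and this is the only one of the tanning comparisons to which a time point is attached. Descriptive summaries are promised (mean and SD, or median and IQR), but no between-arm effect estimate with an interval is named for these two outcomes.

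The protocol shows that baseline values exist:

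- Under Screening Procedures, participants receive "15-minute online baseline surveys including tanning behavior, sun protection behavior, and social networking use".
- The Measures table marks tanning behaviour and "Intentions to Tan" at both baseline and follow-up.
- Follow-Up Assessment describes a "follow-up survey which will assess indoor tanning, outdoor tanning, intention to tan indoors and outdoors".
- Study design fixes the order: "Participation starts with an initial survey, telephone screening, and baseline survey. Eligible participants will then be randomized to one of two conditions".

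Under Data Analysis the protocol says "We will also describe changes from baseline to follow-up in desirability of tanning and alternatives, outdoor tanning". That is a plan to describe these outcomes, and no test is given for them.

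**The concern.** A baseline value of the same outcome, recorded before randomisation, is usually the best available covariate. A rank sum test on follow-up values ignores it. A rank sum test on changes uses it, but with a fixed weight of one that may suit the data poorly. With 30 per arm, or about 24 at the 80% retention benchmark, precision is scarce.

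Two reporting points go with this. A reader has to infer which quantity was ranked, and the two choices differ in power. And a p-value without an estimate and interval does not show how little or how much a pilot of this size can say about the contrast.

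What is at stake is modest. The protocol's Aim lists these outcomes as exploratory, feasibility is judged against the SAP's benchmarks of more than 80%, and the Data Analysis section carries recruitment and retention forward to the efficacy trial.

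**Working it through.** **No power figure to reproduce.** The protocol sizes the pilot at 30 per group (2 × 30 = 60) on feasibility grounds and gives no power calculation.

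**Inputs from the documents:** 30 per arm; 24 per arm at 80% retention (0.8 × 30); both outcomes measured before randomisation and at follow-up; entry rule on tanning likelihood.

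**Inputs assumed:** the correlation between baseline and follow-up, the count distribution, the effect sizes, the intention scale, and a two-sided 5% level. The documents give none of these.

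**Step 1, closed form (normal outcome, equal variances).** The relative variance of the between-arm difference is 1 for follow-up only, 2(1 − ρ) for change and 1 − ρ² for baseline adjustment.

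| ρ | Follow-up | Change | Adjusted | CI width, adjusted vs follow-up |
|---|---|---|---|---|
| 0.3 | 1 | 1.40 | 0.91 | −5% |
| 0.5 | 1 | 1.00 | 0.75 | −13% |
| 0.7 | 1 | 0.60 | 0.51 | −29% |

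The last column is 1 − √(1 − ρ²). Change is worse than follow-up below ρ = 0.5 and better above it. Adjustment is at least as precise as either.

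**Step 2, skewed counts by simulation.** Negative binomial, mean 4 against 2, shape 0.8, 20,000 trials per cell. Power:

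| Latent ρ (Spearman) | n per arm | Wilcoxon, follow-up | Wilcoxon, change | Rank ANCOVA |
|---|---|---|---|---|
| 0.3 (0.27) | 30 | 41% | 28% | 44% |
| 0.5 (0.46) | 30 | 41% | 36% | 50% |
| 0.7 (0.65) | 30 | 41% | 52% | 63% |
| 0.3 | 24 | 34% | 23% | 36% |
| 0.5 | 24 | 34% | 29% | 42% |
| 0.7 | 24 | 34% | 43% | 53% |

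Repeat runs with separate code agreed to within about 2 points. At ρ = 0 with 30 per arm they gave 41% for both the follow-up Wilcoxon and rank ANCOVA, so adjustment cost nothing. Type I error was about 5% for every test.

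**Step 3, intentions.** Assumed 0-10 item, latent mean 5.5 and SD 2.5, baseline kept only above 4, shift of 0.5 latent SD, 30 per arm. Power at ρ 0.3, 0.5, 0.7: follow-up Wilcoxon 47%, 51%, 57%; change 42%, 51%, 69%; rank ANCOVA 49%, 55%, 70%. The entry restriction cut the rank correlation to about 0.20, 0.33 and 0.51.

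**Step 4, an estimate from the same model.** Let p be the chance that a sun safety participant has a higher value than a control participant, ties counted half. The mean overall ranks are (n₁ + 1)/2 + n₀p in the sun safety arm and (n₀ + 1)/2 + n₁(1 − p) in the control arm. Their difference is (n₁ − n₀)/2 + n₀p − n₁(1 − p) = N(p − 0.5), with N = n₁ + n₀. So p = 0.5 + difference/N, and the adjusted version replaces the difference by the condition coefficient of the rank ANCOVA. For a halving of counts the true value is 0.372 and the mean adjusted estimate was 0.371-0.372. Coverage of the 95% interval was 94.9-95.5% for counts and 94-96% for the bounded intention item. For counts at 30 per arm the median half-width falls from 0.144 to 0.140, 0.129 and 0.110, that is by 3%, 10% and 24%.

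**The case against.** **Nothing is invalid.** This stands. A reader might infer that chance baseline imbalance makes the Wilcoxon tests unsafe. In the count simulation at ρ = 0.7 and 30 per arm, false positives are 11.2% in the third of trials with imbalance above 0.25 SD, but 1.9% in the rest: ⅓ × 11.2% + ⅔ × 1.9% ≈ 5.0%. Overall error is held, so the argument is about precision only.

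**The ambiguity is mild.** This largely stands. The SAP says perceived change when it means change for motivation, times tanned outside is a count, and the next sentence tests the binary form at follow-up. Follow-up values are the natural reading. A reader might see a conflict with the protocol's changes from baseline, but the protocol only describes those changes. Nor can a reviewer declare that follow-up values were used: the SAP is in the past tense, and only the trial team knows.

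**It is a feasibility pilot.** True, and it sets the priority. Yet the SAP chose to test these two outcomes between arms while declining to test others for lack of power. Having tested them, it should show how precise the contrast is.

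**Missing baselines could cancel the gain.** Survey questions may be skipped. With complete cases only, losing 3 of 30 per arm at ρ = 0.3 gives about (44.1% + 36.4%)/2 ≈ 40%, against 41% for the follow-up Wilcoxon on all 30. That holds for a complete-case analysis. In simulation, filling 10% missing baselines with the median kept power at or above Wilcoxon.

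**The size rests on assumptions.** This stands. Low correlation is plausible for intentions, because a participant is excluded if "Likelihood of indoor or outdoor tanning this summer is 4 or less on the scale of 0-10", which narrows the baseline range if the intention item resembles that question.

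**Conclusion.** The point holds as a low-priority improvement. The two Wilcoxon comparisons are valid, but they do not adjust for baseline values that were already collected, and they are not accompanied by a named between-arm estimate. The gain for counts is 2-3 points of power if baseline predicts weakly and about 22 points (41% to 63%) at a latent correlation of 0.7. For intentions it is 2 to 13 points. Even then power stays at or below about 70% for the effects assumed, so the adjustment does not turn the pilot into an efficacy test. The documents support neither a claim of inflated error nor a claim that any feasibility conclusion would change. All sizes depend on the assumed correlations, distributions and effects, and on the baseline items being comparable with the follow-up items. The case for naming the ranked quantity and reporting an interval does not depend on the correlation.

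**What to change.** 1. State which quantity each Wilcoxon test ranked, follow-up value or change, as it was actually done.
2. Beside each test, report a rank ANCOVA: overall rank of the follow-up value on condition and baseline rank only. Leave out gender and region; with up to ten strata for 60 people they would cost more than they return.
3. From the same model, report the adjusted win probability, 0.5 + condition coefficient/N, with its 95% CI from the coefficient's standard error divided by N.
4. Keep participants whose baseline is missing by filling in the baseline median pooled over both conditions.
5. Label the analysis supportive, and post hoc if the data have been seen. Keep the Wilcoxon and chi-squared tests as they are.

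The cost is a few sentences in the SAP and a few lines of SAS, with no new data. The downsides are one more p-value for each exploratory outcome, little gain if the correlation is low, and no way to restore prespecification if results are already known.
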